## **11.3** Planned Interim Analyses

No interim analyses are planned.

#### 11.4 Primary Analysis

#### Primary outcome analyses:

A modified intention to treat approach will be used where subjects will be analyzed according to the group they were randomized provided they have been shipped the drug, taken one dose and completed at least one follow-up assessment.

The proportion of patients who meet the primary outcome will be compared by binomial regression adjusting for stratification and the difference will be reported as an absolute risk difference and 95% CI.

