Exclusion Criteria	
 
Already on inhaled corticosteroid medication
 
Currently using systemic steroids (oral or intravenous or intramuscular such as Prednisone) or use of steroids 7 days prior to enrolment
 
Severely ill patients at enrollment (i.e., admitted to ICU at admission)
 
Unable to self-administer the inhaler
 
Known or suspected pregnancy and breastfeeding
 
Known allergy to study medication or its components (non-medicinal ingredients; including lactose allergy (type I))
 
Patients with untreated fungal, bacterial or tubercular infections of the respiratory tract
 
Current hospitalization
 
Current use of oxygen at home or in hospital
 
Vaccinated for COVID-19
 

Stratification	Randomization will be stratified by sex
Statistical Assumptions	With 159 subjects per arm we will be able to detect an absolute increase of 15% in the number of patients with resolved symptoms at day 7.
Safety	Safety of the intervention will be assessed by the cumulative incidence of Grade 3 and 4 AE and SAEs using the Division of AIDS Table for Grading Severity of Adult and Pediatric Adverse Events version 2.1

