# 7 STUDY SCHEDULE

- Information includes consent document. The patient signs electronically in the application after answering questions which confirm comprehension.
- If eligible, drug is prescribed, they are randomized, and shipping is arranged for study drug or placebo

Questionnaire	Day 0	Day1	Day 3	Day 5	Day 7	Day 10	Day 14	Day 29
Eligibility (screening form)	X							
Enrolment form (for eligible patients)	X							
Follow up questionnaire (MESA COVID 19)	X	X	X	X	X	X	X	X
Severity of overall symptoms	X	X	X	X	X	X	X	X
Dyspnea characteristics	X	X	X	X	X	X	X	X
Dyspnea severity	X	X	X	X	X	X	X	X
Visual analog scale for individual symptoms	X	X	Х	X	X	X	Х	X
Sleep PROMIS scale	X	X	X	X	X	X	X	X
Anxiety PROMIS scale	X	X	X	X	X	X	X	X

WHO ordinal scale	X	X	X	X	X	X	X	X
Hospitalization/Oxygen		X	X	X	X	X	X	X
use query								
Side effects query		X	X	X	X	X	X	X
Mortality							X	X
Subject orientation of							X	
the type of the study								
drug (placebo or active								
drug)								

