#### 7.2 Enrollment/Baseline

## **7.2.1** Randomization (Day 0)

- Medication list and screening form will be reviewed by central physician using the doctor review function in REDCap.
  - O If there are any doubts about the subject's appropriateness, the patient will be called by telephone to obtain more details. The medication list provided by the patient will be specifically reviewed by an expert physician in Internal Medicine who is aware of issues surrounding polypharmacy. Patients who have an unacceptable medical review will be excluded prior to randomization and the reason noted.
- Participants will be randomized by a computer-generated algorithm using a permuted block randomization sequence
- Randomization will be stratified by study site and sex
- Investigational pharmacy will dispense the masked study medicine
- Study personnel will then courier study medicine to the participant
- Participant will be sent an email about when to expect medication to arrive

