#### 7.3 Follow-up

#### Day 0 Virtual questionnaire

• Query for symptom status

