#### Day 1 Virtual questionnaire

- Verify receipt of study medicine
- Clinical status check-in
- Participant starts study medicine Ciclesonide 600mcg BID inhaled with aero chamber plus intranasal ciclesonide 200 mcg DIE

- Confirm the positive SARS-CoV-2 test result
- Query for symptom status
- Assess other medicines used during study period
- self reported hospitalization and oxygen use

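### The primary model leaves out the Day 0 symptom severity already collected, and the strata it adjusts for are not named consistently

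*Combined protocol and SAP*

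**What the plan says.** - **Primary model (Section 11.4).** "The proportion of patients who meet the primary outcome will be compared by binomial regression adjusting for stratification", with the result reported as an absolute risk difference and 95% CI. The secondary proportions use the same unnamed adjustment. No baseline severity term appears in either.
- **Baseline data (Section 7, study schedule).** "Severity of overall symptoms" and "Dyspnea severity" are both marked at Day 0.
- **Timing (Section 7.3).** "Participant starts study medicine" is listed under Day 1. However, Section 7.2.1 places randomisation itself on Day 0, and the "Day 0 Virtual questionnaire" is listed under Follow-up.
- **Strata.** The Summary says "Randomization will be stratified by sex". Section 7.2.1 says "Randomization will be stratified by study site and sex". Section 5.3.1 mentions permuted blocks and names no factor.

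**The concern.** There are two separate points.

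First, how severe symptoms are at entry plausibly predicts whether they have cleared by Day 7. If so, adjusting for entry severity narrows the confidence interval of the primary risk difference with no new data. If not, the cost is negligible.

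Second, the model adjusts for stratification, but the documents disagree on what the strata are. Two analysts following Section 11.4 could fit different primary models: one with sex, the other with sex and site.

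What is at stake is some precision and a fully specified model. Validity is not in question.

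**Working it through.** **Inputs from Section 11.2.** Resolution by Day 7 of 65% (placebo) and 80% (ciclesonide), 80% power, 5% alpha, 15% dropout, 159 per arm, 318 in total.

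**The plan's own figure.** Two proportions, pooled variance under the null, two-sided 5%, mean rate 0.725:

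n = [1.960 × √(2 × 0.725 × 0.275) + 0.842 × √(0.65 × 0.35 + 0.80 × 0.20)]² / 0.15² = 137.9, so 138 per arm and 276 in total, as in the plan's table.

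Allowing for dropout, 138 × 1.15 = 158.7, so 159 per arm and 318 in total. The plan's figures reproduce exactly. With 15% lost, 159 × 0.85 = 135 per arm remain.

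**Unadjusted baseline.** Closed-form power is about 79% at 135 per arm and 85.3% at 159. The CI half-width at 135 is 1.96 × √[(0.2275 + 0.16)/135] = 0.105, or 10.5 points.

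**Adding one Day 0 covariate, by simulation.**
- *Assumptions:* permuted blocks of 4 within sex by site; three sites split 70/20/10; strata not prognostic; one standard-normal Day 0 score; marginal rates held at 65% and 80%.
- *Model:* logistic, with arm, sex, two site terms and the score. That is 6 coefficients for about 74 expected non-resolvers (135 × 0.35 + 135 × 0.20).
- *Estimate:* standardised to a risk difference, with an influence-function standard error (divisor n − k). There were 8,000 to 10,000 trials per setting.

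| Assumed log-odds per SD | Within-arm AUC | Power, strata only, 135/arm | Power, adjusted, 135/arm | Change (points) | Adjusted CI half-width (points) | Change at 159/arm (points) |
|---|---|---|---|---|---|---|
| 0 | 0.50 | 79.9% | 79.9% | 0.0 | 10.5 | +0.1 |
| 0.3 | 0.58 | 80.2% | 80.6% | +0.4 | 10.4 | +0.6 |
| 0.5 | 0.64 | 79.8% | 81.2% | +1.4 | 10.3 | +1.3 |
| 0.7 | 0.68 | 80.5% | 83.8% | +3.3 | 10.1 | +2.0 |
| 1.0 | 0.74 | 80.0% | 85.9% | +5.9 | 9.7 | +4.6 |

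The Monte Carlo standard error of the changes is 0.1 to 0.3 points. The ratios of adjusted to strata-only variance at 135 per arm are 1.003, 0.989, 0.965, 0.921 and 0.852.

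**Closed-form cross-check.** If the covariate explains a share R² of outcome variance, the effective sample size is n/(1 − R²). From 79.2% at 135 per arm, power becomes 80.0% at R² = 0.02, 81.2% at 0.05, 83.3% at 0.10 and 87.4% at 0.20. The direction and rough size agree.

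**Robustness at 135 per arm, log-odds 0.5, 0.7 and 1.0.**
- Four-level severity scale, scored linearly: +1.6, +2.5, +4.7 points.
- Three skewed levels: +1.5, +2.6, +4.6.
- 10% of Day 0 values missing and set to the overall mean: +1.3, +2.6, +5.0.
- Sex as the only stratum: +1.5, +3.2, +5.5.

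With a useless covariate, the largest loss across these settings was 0.2 points.

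**Type I error at 65% in both arms (20,000 trials, log-odds 0, 0.5 and 1.0).** Strata-only 5.2, 5.2 and 5.1%; adjusted 5.3, 5.1 and 5.1% (Monte Carlo standard error 0.16).

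**Leaving site out of the model.** With the same assumed three sites and site rates differing by up to ±15 points, a linear risk-difference model with robust errors has a standard error 0.2 to 1.6% too large. Power stays within 0.7 points.

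**The case against.** The planned analysis is valid without the covariate, so this is an efficiency choice and not a defect. **That stands**, and it is why the point is graded as advisable and not essential.

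The documents give no prognostic strength for Day 0 severity. Eligibility is limited to mild disease and excludes hospitalised and oxygen-using patients, which narrows the severity range and makes the upper end less likely. **That also stands.** At log-odds 0.3 to 0.5 the gain is only +0.4 to +1.4 points.

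Section 5.3.3 replaces withdrawn participants up to 318. If that works, the 159-per-arm column applies, power already starts near 85%, and the gains are mostly smaller. Section 5.3.3 also mentions 25% dropout. That would leave about 119 per arm and 74.0% power unadjusted, a case in which extra precision is worth more.

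The change may come too late. The DSMB section is written in the past tense, and time to symptom resolution is already labelled post hoc. Unblinding status is not stated, so the recommendation has to depend on it.

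The type I error result used the n − k divisor. Smaller runs gave adjusted rates up to 5.7% with it. Without it, one run gave 5.6 to 5.8% (5.4% with it) and another 5.1 to 5.6% (4.9 to 5.4% with it). These differences are of the order of simulation error, but the divisor should be stated.

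Finally, the strata discrepancy is largely clerical. One sentence settles it, and it would not merit a comment by itself.

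**Conclusion.** The concern holds, as a modest improvement. The primary model omits a baseline severity measure the trial already collects, and its strata are undefined because the Summary and Section 7.2.1 differ.

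At 135 evaluable per arm, the gain from one Day 0 covariate is about 0 to 6 points of power and up to 0.8 points of CI half-width. At 159 per arm it is about 0 to 5 points of power. The range rests on assumed log-odds of 0 to 1.0 per SD and on an assumed site structure. The loss if severity is uninformative is at most 0.2 points in simulation.

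The sample size calculation is not in question, and neither point biases the risk difference.

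**What to change.** 1. Make the Summary, Section 5.3.1 and Section 7.2.1 agree on the strata actually used in the randomisation. Name them in Section 11.4 for both the primary and secondary analyses, with a rule for pooling small sites.
2. Before unblinding, prespecify one Day 0 covariate in the primary model. Overall symptom severity is the natural choice because the endpoint covers several symptoms; dyspnea severity is the alternative.
3. Require the value to be recorded before randomisation, or at least before the participant receives medicine. Replace a missing or late value by the mean over both arms, so that nobody is dropped.
4. Keep the absolute risk difference as the estimand, standardised from a logistic model with a robust 95% CI, and state the n − k divisor. This also avoids the convergence problems an identity-link binomial model can have with a continuous covariate or several site terms.
5. Keep the strata-only model as a sensitivity analysis. If the data are already unblinded, reverse the roles: strata-only stays primary and the adjusted result is labelled post hoc.

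The cost is plan wording and a few lines of code. No new data are needed.

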#### **Secondary Analyses:**

Proportions meeting each secondary outcome will be analyzed by binomial regression adjusting for stratification and the differences will be reported as an absolute risk difference and 95% CI.

The post-hoc analysis of time to symptom resolution will use the Kaplan Meier plot.

#### Handling of withdrawn subjects.

If there is a large lost to follow up / study discontinue rate, then the primary endpoint would have a secondary analysis to assess incidence as a 3-category analysis of: i) increase in disease symptoms, ii) decrease in disease symptoms, iii) no change in disease symptoms or iiii) unknown.

Participants who stop taking the study medicine but who agree to be followed for the duration of the study will be assessed as intent-to-treat. On Day 1, 3, 5, 7, 14 and 29, we will ask for other medications or vitamins that were taken during the study period.

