#### **3.2** Study Outcome Measures

#### **3.2.1** Primary Outcome Measures

**Primary outcome** is defined as the proportion of patients with resolved respiratory symptoms (fever, cough, shortness of breath, chest congestion or chest tightness) at day 7.

[figure not shown]

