#### **9.2.3** Serious Adverse Events (SAEs)

SAEs (e.g. hospitalization) will be followed for up to 29 days to assess final outcome.

A patient who reports hospitalization and/or an adverse effect of the study drug on a CRF who has not reached out to the team by phone or email will be contacted in a timely fashion and the site doctor made aware. We will review the "positive" CRFs to detect these. We also collect details about the hospitalization.

Patients who do not complete their day 14 CRF will receive reminder emails and, if they do not respond to that, they will be telephoned. Patients must provide an alternate contact at enrollment. If they do not respond to the above means, we will call that contact to find out what has happened. If that person does not know or is not available, we will send registered mail to the address of the patient before concluding loss to follow-up. A sensitivity analysis of the mortality outcome will be performed assuming patients lost to follow-up despite these means have died.

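### The back-up analysis for loss to follow-up does not identify day-7 resolution and has an undefined trigger, so it cannot show whether the primary risk difference survives missing data

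*Combined protocol and SAP*

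**What the plan says.** Section 3.2.1 defines the primary outcome as the "proportion of patients with resolved respiratory symptoms (fever, cough, shortness of breath, chest congestion or chest tightness) at day 7". Section 11.4 says the proportions will be "compared by binomial regression adjusting for stratification and the difference will be reported as an absolute risk difference and 95% CI". Patients are analysed as randomized "provided they have been shipped the drug, taken one dose and completed at least one follow-up assessment". That follow-up assessment need not be the day-7 one, so a patient with no day-7 answer can be in the analysis set. Section 11.4 gives no rule for scoring such a patient.

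The provision for missing data on this endpoint comes under Handling of withdrawn subjects: "If there is a large lost to follow up / study discontinue rate, then the primary endpoint would have a secondary analysis", described as a "3-category analysis of: i) increase in disease symptoms, ii) decrease in disease symptoms, iii) no change in disease symptoms or iiii) unknown". The paragraph gives no threshold for *large*, and does not say who judges it or on what data. It names no time point, symptom measure, test or effect measure.

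Elsewhere, section 9.2.3 has an explicit missing-data analysis, but for another endpoint: "A sensitivity analysis of the mortality outcome will be performed assuming patients lost to follow-up despite these means have died". Section 11.2 allows for 15% dropout; section 5.3.3 gives both 15% and 25%. Sections 5.3.4 and 11.4 keep following patients who stop the drug.

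**The concern.** A robustness analysis should re-estimate the primary quantity under different assumptions about the outcomes not seen. This one changes the outcome instead. A patient whose cough goes from severe to mild is a decrease here and a failure in the primary analysis. A patient whose symptoms have gone would normally be a decrease too. Patients with no data go to unknown with no outcome assumed for them.

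The trigger is a second weakness. With no number attached to *large*, nothing fixes in advance whether the analysis is done. It also joins two different events: a patient lost to follow-up has no day-7 outcome, while a patient who stops the drug may still supply one.

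All outcomes are self-reported online, so missed forms are a realistic risk. If a positive result were reported, the planned back-up could neither support it nor show it to be fragile.

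**Working it through.** **1. The plan's own figure.** Inputs from section 11.2: 65% versus 80% resolved, 80% power, alpha 0.05 (taken as two-sided). With the pooled-variance formula, the mean proportion is 0.725 and

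n = [1.960 × √(2 × 0.725 × 0.275) + 0.842 × √(0.65 × 0.35 + 0.80 × 0.20)]² / 0.15² = 138 per arm, or 276 in total.

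Then 138 × 1.15 = 158.7, so 159 per arm and 318 in total. Both stated figures reproduce, and I use 65%, 80% and 159 below.

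**2. What the categories can show.** Suppose 90% of each arm is classed as a decrease. This is compatible with 80% resolved plus 10% partly improved on active, and 65% resolved plus 25% partly improved on placebo. The category table shows no difference; the primary risk difference is 15 points. The primary estimate cannot be recovered from the table.

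**3. Extreme-case bounds.** Assume a fraction m of day-7 outcomes is missing in each arm, with 80% and 65% resolved among those observed.

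- Lower bound (missing active all unresolved, missing placebo all resolved): 0.80(1 − m) − [0.65(1 − m) + m]
- Upper bound (the reverse): [0.80(1 − m) + m] − 0.65(1 − m)

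| m | Lower (points) | Upper (points) |
|---|---|---|
| 5% | 9.25 | 19.25 |
| 10% | 3.5 | 23.5 |
| 15% | −2.25 | 27.75 |

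**4. Less extreme assumptions.** Take 159 per arm as the analysis set, whole-number counts, and an unadjusted Wald 95% CI, d ± 1.96 × √[p₁(1 − p₁)/n + p₂(1 − p₂)/n]. For the last column, missing placebo patients resolve at 65% and the rate among missing active patients is lowered in steps of one percentage point until the CI includes zero.

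| Missing per arm | Resolved/observed, placebo; active | Observed only, points (95% CI) | Missing = not resolved, points (95% CI) | CI first includes zero when missing active resolve at |
|---|---|---|---|---|
| 5% (8) | 98/151; 121/151 | 15.2 (5.3 to 25.2) | 14.5 (4.4 to 24.5) | never |
| 10% (16) | 93/143; 114/143 | 14.7 (4.5 to 24.9) | 13.2 (2.8 to 23.6) | about 33% |
| 15% (24) | 88/135; 108/135 | 14.8 (4.3 to 25.3) | 12.6 (2.0 to 23.2) | about 47% |
| 25% (40) | 77/119; 95/119 | 15.1 (3.9 to 26.3) | 11.3 (0.4 to 22.2) | about 59% |

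Check of the 15% row: placebo (88 + 0.65 × 24)/159 = 0.652; active (108 + 0.47 × 24)/159 = 0.750; difference 9.9 points, CI −0.1 to 19.9.

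These intervals treat filled-in outcomes as if observed, so they are somewhat narrow. An analysis that carried the imputation uncertainty would reach zero a little sooner.

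**The case against.** Several points on the other side have force.

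- **The trigger.** A reader might infer that it is set after seeing results. The documents do not say so. *Large* is undefined, and the monthly progress report in section 15.4 lists loss to follow-up, so the rate could be judged without day-7 results by arm. What stands is that the trigger is undefined and combines two events.
- **The missing rate.** A reader might take 15% as the expected share of missing day-7 outcomes. It is a dropout allowance. Section 5.3.3 defines withdrawal as ending treatment, though it later equates dropping out with loss to follow-up, and it also cites 25%. Some patients who stop the drug will have day-7 data, and some losses fall outside the modified intention-to-treat set. The true fraction is unknown, so the figures above are illustrative.
- **The bounds.** They are extreme. The point difference stays positive at 5% and 10% missing, and counting all missing as not resolved keeps the CI above zero throughout. A claim that missing data would remove the effect is not supported. The tipping points show only that it could, under assumptions short of the extreme.
- **Other analyses.** The Kaplan-Meier analysis of time to symptom resolution is on the resolution scale and can use partial follow-up. But it is labelled post hoc and does not test whether missingness depends on outcome. Continued follow-up after stopping the drug reduces missing data but does not test its effect.
- **Three categories or four.** Calling it a 3-category analysis and listing four is editorial: it reads naturally as three symptom categories plus unknown. Showing unknowns by arm is useful in itself.

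**Conclusion.** The point holds. The only missing-data analysis stated for the primary endpoint does not use the resolved / not-resolved outcome, so it cannot show whether the section 11.4 risk difference survives missing day-7 data. Whether it runs at all depends on an undefined trigger.

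The size depends on assumptions that the documents do not settle: equal missingness in both arms, design-value rates among those observed, 159 analysed per arm and an unadjusted interval. On these, the result is robust at 5% missing and sensitive to plausible departures at 25%, where a rate of about 59% rather than 65% among missing active patients is enough for the CI to include zero. A proper check could therefore strengthen the conclusion or weaken it.

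The primary analysis can be run as planned, so this is a change that should be made rather than a fatal flaw.

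**What to change.** Amend the paragraph on withdrawn subjects in section 11.4 as follows.

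1. Whatever the loss rate, repeat the primary risk difference and 95% CI on the resolved / not-resolved day-7 outcome in the modified intention-to-treat set:
   - (a) with missing day-7 status counted as not resolved, unless the plan adopts that as its primary rule;
   - (b) as a tipping-point table that varies the resolution rate among missing patients separately in each arm and reports where the 95% CI first includes zero.
2. Remove the *large* trigger.
3. The category table may stay as a description of unknown outcomes by arm, but not as the robustness check.

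This costs SAP wording and one extra table from data already held, with no new visits or participants. The drawback is that the result may look less secure.

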# 12 SOURCE DOCUMENTS AND ACCESS TO SOURCE DATA/DOCUMENTS

Source documents will include internet forms self-completed by participants directly entered into a REDCap database.

This protocol is based on self-report.

This internet-based protocol is meant to enable a large number of participants to be recruited, quickly as well as maintain the safety of the research staff. In person visits, create a public health risk due to transmission of COVID-19 from unrecognized cases. Likewise, paper documents and consent forms also carry this risk (as fomites) and so all consent documentation will be recorded electronically with an online signature.

Participants will be asked to provide consent to obtain medical records from their healthcare provider or public health official, if there is the need to verify outcomes – for SARS-CoV-2 test results or hospitalizations.

